9.3 POPULATIONS FOR ANALYSES

Participants with post-stroke aphasia

9.4 STATISTICAL ANALYSES

9.4.1 GENERAL APPROACH

Please see specific information below.

9.4.2 ANALYSIS OF THE PRIMARY ENDPOINT(S)

We will code each trial in the EMA time series to index compliance, completion, and speech intelligibility. Every scheduled trial (n = 756 total trials) will be coded as 0 for a nonresponse/ NO button

Version 1.000

Protocol 15 March 2022

response or 1 for a YES button response, reflecting compliance. Every delivered trial with a naming attempt captured on audio (n trials will vary by person) will be coded as 0 for incomplete or 1 for complete, reflecting completion. For each of these measures, we will run a logistic mixed effects model with one of the feasibility measures (i.e., compliance, completion) as the dependent variable, condition (1-item vs. 9-item) as the independent variable, and random effects of participant and trial.

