3 OBJECTIVES AND ENDPOINTS

OBJECTIVES	ENDPOINTS	JUSTIFICATION FOR ENDPOINTS	PUTATIVE MECHANISMS OF ACTION
Primary			
Assess EMA compliance in PWA	Compliance will be calculated by dividing the number of answered prompts by the number of scheduled prompts	This metric is often used in describing feasibility of EMA protocols.	N/A - not an intervention
Assess EMA completion in PWA	Completion will be calculated by dividing the number of answered prompts by the number of	Compliance reflects protocol adherence excluding trials missed due to the watch being off/uncharged or a problem with the trial	
	delivered prompts	flow.	
Secondary			
Assess speech intelligibility of EMAs	Recorded responses will be tagged as fully intelligible (1) or partially or completely unintelligible (0)	Speech EMA requires intelligible responses to be clinically useful	N/A - not an intervention
Assess perceived burden from EMAs in PWA	Perceived burden will be calculated by averaging Likert ratings from the Qualtrics survey questions regarding perceived burden	Gathering information about participants experiences with a novel protocol is important for establishing its clinical utility	N/A - not an intervention
Tertiary/Exploratory			
Determine relationships between EMA feasibility metrics and personal factors	N/A	No explicit endpoint are applicable for this objective	N/A - not an intervention

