8.1 ENDPOINT AND OTHER NON-SAFETY ASSESSMENTS

Endpoint Assessments: Feasibility will be classified in three ways: (1) PWAs' adherence to the smartwatch μΕΜΑ or EMA protocol via compliance and completion, (2) PWAs' perceived burden of completing the EMA protocol, and (3) speech intelligibility of recorded naming attempts. Currently, PWAs' capacity for adhering to a smartwatch EMA protocol via button press responses or verbal responses is unknown. As such, compliance will be based on the number of YES button responses to the "Ready?" screen whereas completion will be based on naming attempts. Specifically, similar to [name] et al. (2016), compliance will be determined by the number of YES responses over scheduled trials, including trials missed due to the watch being off/uncharged. Completion will be calculated as trials with captured audio (reflecting attempted naming) over delivered trials, excluding trials missed to the watch being off/uncharged. Perceived burden will be measured via responses to the weekly surveys during weeks 2-4. Finally, speech intelligibility will be measured by a categorical rating of responses captured in each audio clip (i.e., completely intelligible, partially intelligible, or completely unintelligible).

Other Non-Safety Assessments: Before the EMA period, PWA will be administered the following testing battery. The Quick Aphasia Battery (QAB) will be used as our eligibility assessment and to measure overall aphasia severity. The Pattern Comparison Processing Speed Test and Flanker Inhibitory Control and Attention Test from the NIH Cognition Toolbox will be used to measure non-linguistic visual attention and executive functions, respectively. We will use brief, standardized picture description and story elicitation tasks from the AphasiaBank protocol to index anomia in discourse. Participants will complete an overt object naming test twice before EMA and once after EMA so that the research team can evaluate word retrieval via the standard SLP assessment format (i.e., single administration in a quiet 1:1 interaction). This picture naming probe will include normed real photos of the 260 items from the Snodgrass and Vanderwart stimuli set. Before EMA, PWA will also participate in an intake interview and complete a questionnaire about their comfort with technology, adapted for aphasia (simple language, short phrases).

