9 STATISTICAL CONSIDERATIONS

9.1 STATISTICAL HYPOTHESES

- Primary Efficacy Endpoint(s): Compliance and completion will be significantly higher for participants who complete the 1-item EMA condition versus participants who complete the 9-item EMA condition.
- Secondary Efficacy Endpoint(s): Speech intelligibility will be over 80% across trials. Perceived burden will not significantly differ between participants who complete the 1-item versus 9-item EMA conditions.

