9.2 SAMPLE SIZE DETERMINATION

For the Aim #1 logistic mixed effects models, two groups of 10 PWA per group will achieve 80% power to detect an odds ratio of 1.20 in a design of 756 repeated measures with a AR(1) covariance structure and when the correlation between observations of the same subject is 0.600 and alpha is 0.05. If the proportion of completed trials for the EMA group is 0.500, a statistically significant result will occur if the μ EMA group proportion is 0.545 or greater. In [name] et al.4, the mean difference in proportions between the μ EMA and EMA conditions was >0.20 for compliance and completion, which is much higher than the needed 0.045 difference. This suggests we will have ample power to detect significant differences between the two conditions.

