9.4.9 EXPLORATORY ANALYSES

We will conduct a series of partial correlations between patient-specific factors and feasibility measures (compliance, completion, speech intelligibility, and perceived burden), controlling for study condition. Patient-specific factors will include age, aphasia severity (derived from the QAB), non-linguistic cognitive skills (averaged performance on the two NIH Toolbox tasks), and a summary score derived from the

Version 1.000

Protocol 15 March 2022

comfort with technology survey. Here, compliance will be the proportion of YES button responses divided by total scheduled trials (YESbutton/756) for each participant. Completion will be the proportion of naming attempts divided by total delivered trials (n naming attempts/n trials delivered). Speech intelligibility will be the proportion of completely intelligible responses divided by the total number of naming attempts (n completely intelligible trials/n naming attempts). Perceived burden will be calculated as the sum of all burden question Likert responses. Multiple comparison correction will be done at a false discovery rate of p < 0.05.

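### The primary completion model in Section 9.4.2 keeps only trials that already count as completed, so its outcome is always 1

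*Combined protocol and SAP*

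**What the plan says.** Section 9.4.2 opens broadly: "We will code each trial in the EMA time series to index compliance, completion, and speech intelligibility". For compliance, every one of the 756 scheduled trials is a row, and a missing response or a NO counts as 0. For completion the row set is narrower: "Every delivered trial with a naming attempt captured on audio (n trials will vary by person) will be coded as 0 for incomplete", with 1 for complete. Each outcome then goes into a logistic mixed model with condition as the explanatory variable and random effects for participant and trial.

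Completion is defined elsewhere as a proportion of delivered trials:

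- Section 8.1: "Completion will be calculated as trials with captured audio (reflecting attempted naming) over delivered trials". Only trials missed because the watch was off or uncharged leave the denominator.
- Section 9.4.9: "Completion will be the proportion of naming attempts divided by total delivered trials".
- Section 3, in prompts: "Completion will be calculated by dividing the number of answered prompts by the number of" delivered prompts (the table cell is split in the text).

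The hypothesis in Section 9.1 is "Compliance and completion will be significantly higher for participants who complete the 1-item EMA condition" than for those in the 9-item condition. Section 9.2 plans on that contrast: "If the proportion of completed trials for the EMA group is 0.500, a statistically significant result will occur" at 0.545 or more in the other group.

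**The concern.** The restriction in 9.4.2 selects trials on the event that the outcome is meant to record. A delivered trial enters the completion model only if a naming attempt was captured. Under 8.1 and 9.4.9, a captured attempt is what makes a trial complete. The plan does not say what an incomplete trial would be among those that remain.

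Completion is one of the two measures in the primary endpoint. If 9.4.2 is followed, that measure does not vary, and the 1-item and 9-item conditions cannot be compared on it. The exploratory correlations in 9.4.9 would meanwhile report completion values that differ between the same participants. An analyst would notice as soon as the model was run, but the row set of a primary outcome would then be chosen with the data in hand. Section 6.3 states that there is no blinding.

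**Working it through.** **Inputs.** Row set: 9.4.2. Event and denominator: 8.1 and 9.4.9. Planning values: 9.2 (10 participants per group, 756 repeated measures, AR(1) correlation 0.600, odds ratio 1.20, alpha 0.05, proportions 0.500 and 0.545).

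**Step 1: the plan's own figure.**

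- An odds ratio of 1.20 from 0.500 gives 1.2/2.2 = 0.5455. With the rounded value, (0.545/0.455)/(0.5/0.5) = 1.20.
- AR(1) variance inflation: 1 + 2 × Σ(1 − k/756) × 0.6^k for k = 1 to 755, which is 3.990.
- Effective observations per group: 10 × 756/3.990 = 1,894.7.
- Two-sided power for 0.500 against 0.5455: 0.8001, which matches the stated 80%. One-sided power would be 0.876, which does not match.

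This shows only that the plan works with completion proportions well below 1, which requires rows coded 0. It is not a judgement on the correlation assumption.

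**Step 2: the two row sets.** Let a participant have D delivered trials and A naming attempts.

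| | Rows | Coded 1 | Coded 0 | Proportion |
|---|---|---|---|---|
| 8.1 and 9.4.9 | D | A | D − A | A/D |
| 9.4.2 as written | A | A | 0 | A/A = 1 |

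The second line holds for any participant with at least one attempt, whatever D and A are.

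**Step 3: at the planning values, assuming all 756 trials are delivered.**

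- 9-item: 378/756 = 0.500, with 378 zeros. On the 9.4.2 rows: 378/378 = 1.000, with none.
- 1-item: 412/756 = 0.545, with 344 zeros. On the 9.4.2 rows: 412/412 = 1.000, with none.

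**Step 4: other assumed values.**

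| Completion, 9-item vs 1-item | Odds ratio on delivered trials | On 9.4.2 rows |
|---|---|---|
| 0.500 vs 0.545 | 1.20 | 1.000 vs 1.000, undefined |
| 0.500 vs 0.700 | (0.7/0.3)/(0.5/0.5) = 2.33 | 1.000 vs 1.000, undefined |
| 0.30 vs 0.50 | (0.5/0.5)/(0.3/0.7) = 2.33 | 1.000 vs 1.000, undefined |
| 0.70 vs 0.90 | (0.9/0.1)/(0.7/0.3) = 3.86 | 1.000 vs 1.000, undefined |

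The 0.20 gap in the last three rows is the lower bound that 9.2 cites from the earlier study. Incomplete delivery does not change the result. With 90% delivered (680.4 trials) and completion of 0.5 to 0.7, the full row set has 340 to 204 zeros per participant; the 9.4.2 set has none.

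**Step 5: could incomplete mean something else?** Section 6.1.2 starts the recording when the participant taps YES, so a clip may hold no speech. But 9.4.2 asks for a naming attempt, not merely a recording. Even on a looser reading, delivered trials with no response or a NO would be left out, giving completion among trials answered YES, which is not the 8.1 endpoint. Intelligibility cannot be the meaning either, because 9.4.3 analyses it as a separate outcome on the same clips.

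**The case against.** The best reply is that nobody would carry out 9.4.2 literally. The sentence contains a 0 code that would be empty, its opening refers to each trial in the series, and 8.1 and 9.4.9 both give the denominator as delivered trials. The contradiction is visible and the correction is already in the document, so little room for choice remains. This stands as evidence of intent, and it is why the point is treated as a drafting slip. It does not make the sentence correct, and 9.4.2 is the only place where the primary completion model is specified. An improvised repair could also go more than one way. With assumed counts of 756 scheduled, 700 delivered, 400 answered YES and 350 attempts, completion is 350/700 = 0.50, 350/400 = 0.875 or 350/756 = 0.46. Only the first has support in 8.1 and 9.4.9, which is a reason to write it down.

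Two further points are fair. First, 9.2 uses the scheduled count of 756 and discusses compliance and completion together, so 0.500 and 0.545 are general planning values and weaker evidence of the completion denominator. The finding does not need them: A/A = 1 follows from the definitions alone. Second, coding a silent clip as 0 needs someone to listen, whereas 6.2.1 describes completion data as recorded automatically. That is true, but the same section already has one rater assess all samples.

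**Conclusion.** The concern holds. Followed as written, the completion outcome equals 1 in every row of both conditions, the condition odds ratio is undefined, and the completion half of the 9.1 hypothesis cannot be tested. The result rests only on the 8.1 and 9.4.9 definition of completion and on the absence of any other meaning for an incomplete trial. It does not depend on the completion rate, the number of trials delivered or the sample size calculation. The compliance model is unaffected.

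It should be fixed before analysis: intent is clear from the rest of the plan, but the rule for a co-primary outcome is wrong in the one place that specifies its model. The Section 3 differences are matters of wording. The justification in the completion row reads "Compliance reflects protocol adherence excluding trials missed due to the watch being off/uncharged", while 8.1 counts those trials in the compliance denominator. The word prompt is also used loosely: Section 1.3 counts 18 prompts in both conditions.

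**What to change.** Replace the completion sentence in 9.4.2 with one to this effect: each delivered trial is one row, coded 1 when a naming attempt was captured on audio and 0 in all other cases (no response, a NO, or no attempt after a YES). This is the definition already used in 8.1 and 9.4.9.

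In Section 3, state completion at trial level as in those sections, and let the justification in that row refer to completion rather than compliance. Stating the compliance row in trials as well would keep the table in one unit.

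Two details are worth a line each, although they are not part of this error: how a clip without speech is identified, and whether an unanswered 9-item prompt counts as nine delivered trials.

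The cost is wording only. Sections 8.1 and 9.4.9 already require the number of delivered trials per participant, and all audio samples are already rated. No extra data collection, staff or sample size change is needed.

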6 STUDY INTERVENTION(S) OR EXPERIMENTAL MANIPULATION(S)

6.1 STUDY INTERVENTION(S) OR EXPERIMENTAL MANIPULATION(S) ADMINISTRATION

6.1.1 STUDY INTERVENTION OR EXPERIMENTAL MANIPULATION DESCRIPTION

Participants will be pseudo-randomly assigned to either the 1-item EMA condition (n = 10) or 9-item EMA condition (n = 10). For every prompt, the smartwatch will vibrate to alert the participant to a prompt to complete either a single picture naming trial (in the 1-item condition) or a set of picture naming trials (in the 9-item EMA condition). Participants in both conditions will be scheduled to complete 36 overt picture naming trials per day for three weeks. The only difference between conditions will be the trial delivery schedule: PWA in the 1-item condition will complete a single naming trial at a time, 36 times per day whereas PWA in the 9-item EMA condition will receive four prompts per day to complete a set of nine picture naming trials per prompt. The twofold rationale for comparing 1-item and 9-item EMA conditions is that we will be able to ensure the results reflect the viability of either delivery schedule specifically and not just the novelty of smartwatch use, and this approach will provide preliminary data regarding which method works best for which PWA.

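### The primary mixed models compare 10 with 10 participants with no small-sample method and no adjustment for the balancing factor, so the 5% error rate is not secured in either direction

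*Combined protocol and SAP*

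**What the plan says.** Section 6.1.1 assigns each participant to one delivery schedule for the whole three weeks, 10 to each. Sections 1.1 and 6.3 add that assignment is pseudo-random and balanced on overall aphasia severity, but give no algorithm.

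Section 9.1 makes the primary hypotheses inferential: "Compliance and completion will be significantly higher for participants who complete the 1-item EMA condition" than in the 9-item condition. Section 9.2 claims that "two groups of 10 PWA per group will achieve 80% power to detect an odds ratio of 1.20". The calculation takes 756 trials per participant with first-order autoregressive dependence, and its remaining inputs are these: "correlation between observations of the same subject is 0.600 and alpha is 0.05".

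For each primary measure section 9.4.2 says "we will run a logistic mixed effects model", with condition as the only fixed effect and random effects of participant and trial. It does not say how the condition effect is tested. No section gives a degrees-of-freedom method, bootstrap or permutation test, and section 9.4.1 only points to the sections after it. Severity enters only the exploratory correlations in section 9.4.9.

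**The concern.** Condition never changes within a person. However many of the 756 trials each participant contributes, the comparison is between 10 people and 10 others, with 18 residual degrees of freedom. The usual outputs of a logistic mixed model, Wald z and the likelihood-ratio chi-square, use large-sample references and a maximum-likelihood variance that in effect divides by 20 rather than 18. Both features favour rejection.

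A second feature works in the opposite direction. When allocation is balanced on a factor that predicts the outcome and the model leaves that factor out, the model's standard error includes variation that the design has largely removed from the treatment contrast. The test then becomes conservative.

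The p-values and intervals for the two primary comparisons are at stake. Section 6.1.1 wants these comparisons to give preliminary evidence on which schedule suits which participants.

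**Working it through.** **Inputs.** From section 9.2: 10 per group, 756 repeated measures, AR(1) correlation 0.6, proportions 0.500 and 0.545, odds ratio 1.20, alpha 0.05, power 80%. Sidedness is not stated. The between-participant SD on the logit scale and the share R² of between-participant variance explained by severity are not in the documents. Both are assumed over a range.

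**1. The plan's own figure.** The AR(1) design effect is 1 + 2·Σ(1 − k/756)·0.6^k = 3.99, so each arm has 7,560/3.99 ≈ 1,895 effective trials. A two-sided normal comparison of 0.500 with 0.5455 (odds ratio 1.20) then gives power 0.800. One-sided gives 0.876. The stated 80% is therefore reproduced as a two-sided large-sample z calculation with no allowance for 18 df. Referring the same effect and standard error to t on 18 df gives 0.754.

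**2. Size of the default tests if severity has no effect.** With this many trials per person, the condition test behaves like a comparison of 10 with 10 participant logits.
- Wald z: P(|t₁₈| > 1.96·√(18/20)) = P(|t₁₈| > 1.859) = 0.079.
- Likelihood ratio: P(|t₁₈| > √(18·(e^(3.841/20) − 1))) = P(|t₁₈| > 1.952) = 0.067.

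Null simulations of a random-intercept logistic model (10 v 10, 756 trials each, 10,000 replicates in each of 7 scenarios) gave 0.078–0.083 for Wald z and 0.064–0.070 for the likelihood ratio. These were stable over participant SD 0 to 1.5, mean response 0.50 or about 0.73, and AR(1) correlation 0 or 0.6. Under section 9.2's own assumptions (correlation 0.6, no further participant variance) they were 0.0775 and 0.066. The simulations left out the random effect of trial. If trial is a position shared by all participants, it is balanced across arms and largely cancels from the contrast.

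**3. Effect of balancing on severity without adjusting for it.** Assumption: participants are matched in close pairs on severity and randomised within pair, with normal participant logits (100,000 replicates).

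| R² of severity | Wald z | Likelihood ratio | Unadjusted t, 18 df |
|---|---|---|---|
| 0 | 0.080 | 0.067 | 0.050 |
| 0.10 | 0.066 | 0.055 | 0.040 |
| 0.20 | 0.052 | 0.042 | 0.030 |
| 0.25 | 0.046 | 0.037 | 0.026 |
| 0.50 | 0.018 | 0.014 | 0.009 |

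Looser matching would offset less.

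**4. Candidate fixes.** A severity-adjusted t-test on participant values with 17 df held 0.049–0.051 at R² of 0.10, 0.20 and 0.25. Adding severity while keeping the default tests is not enough. The argument of step 2 with 17 df gives P(|t₁₇| > 1.96·√(17/20)) = P(|t₁₇| > 1.807) = 0.088 for Wald z, and P(|t₁₇| > √(17·(e^(3.841/20) − 1))) = P(|t₁₇| > 1.897) = 0.075 for the likelihood ratio. Adjustment and a small-sample reference are needed together.

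**The case against.** The strongest objection is that the plan commits to no test, so the liberal behaviour belongs to defaults that a reviewer has supplied. In addition, the severity balancing could offset it. At R² = 0.20, a correlation of about 0.45, the Wald test is close to nominal by accident. Section 5.3 expects severe aphasia without a care partner to make participation harder, so a sizeable R² is plausible. This stands, and it limits what can be claimed.

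A reader might infer that any standard output from this model is too liberal. The documents do not support that, because the direction depends on an R² and a closeness of matching that they do not give. A reader might also infer that a claimed 1-item advantage would be false more than 5% of the time. That is wrong for a two-sided test. By symmetry, at R² = 0 false positives in that direction are half the total, about 4.0% (0.079/2) for Wald z or 3.3% (0.067/2) for the likelihood ratio, against 2.5%.

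It can also be said that the trial is a small feasibility study (section 4.4) and that the distortion on the liberal side is at most about 3 percentage points. This bears on the weight of the point, but section 9.1 does set significance claims. Two unquantified errors that may partly cancel do not amount to control of alpha.

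**Conclusion.** The concern holds as a gap in specification with a measurable consequence. At nominal 0.05, the default tests have size about 0.08 (Wald z) or 0.067 (likelihood ratio) if severity is unrelated to the outcome. Under close matching they have about 0.05 or 0.04 at R² = 0.20, and less beyond that.

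The first pair of figures does not depend on the unstated between-participant SD. The second rests on the assumed R² and pair-matching. The documents settle neither, so the true error rate could lie on either side of 5%. The effect is modest and inexpensive to correct, and the correction should be made before analysis.

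**What to change.** In section 9.4.2, add QAB aphasia severity, which is already collected, as a covariate. Name one small-sample method as the source of the primary p-value and interval:
- a t-based comparison of each participant's logit proportion, adjusted for severity, on 17 df; or
- a parametric-bootstrap likelihood-ratio test in the severity-adjusted mixed model.

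A permutation test that reproduces the actual severity-balanced allocation is an alternative once that algorithm is written into section 6.3. State that the test is two-sided, which is what the power figure implies. Do not use an unadjusted 18-df t-test, which is conservative under this allocation. Without a small-sample method, the severity-adjusted mixed model can serve for description only.

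The cost is a sentence or two, a little more analysis code, and slightly wider intervals than the default severity-adjusted model would give. The critical value alone goes from 1.96 to about 2.11 on 17 df. Data collection does not change.
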